E2C2 / 18-007779

Enhanced, EHR-facilitated Cancer Symptom Control (E2C2)
Pragmatic Clinical Trial

NCT03892967

Document Date: 03/04/2025

IRB Minimal Risk Protocol Template

General Study Information

Principal Investigator: [name], MSCE

Study Title: Enhanced, EHR-facilitated Cancer Symptom Control (E2C2) trial

Protocol version number: March 4, 2025 Version 24

Research Question and Aims

Hypothesis: Collaborative care management for control of moderate or worse sleep disturbance, pain, physical function impairment, anxiety, depression, fatigue (SPPADE symptoms), and physical dysfunction among cancer survivors and patients with cancer will improve quality of life, symptom severity, and adherence to cancer treatment, and will also reduce need for acute care.

Aims:

Specific Aim 1. Conduct a cluster randomized pragmatic trial with a stepped wedge design to test the hypothesis that a symptom control-focused E2C2 intervention will significantly reduce SPPADE symptom and physical dysfunction scores; reduce unplanned hospitalizations, emergency department (ED) visits, and intensive care unit (ICU) admissions; improve adherence to cancer therapies; and improve self-reported quality of life.

H1a. SPPADE symptom scores will improve more, relative to prior scores, for patients who have been exposed to the intervention when compared with the improvement of patients that are not exposed.

H1b. Among patients who report moderate or worse symptoms, SPPADE symptom scores will improve more for patients who have been exposed to the intervention when compared with the improvement of patients that are not exposed.

Specific Aim 2. Evaluate the hypothesis that use of a multifaceted, evidence-based implementation strategy to support adoption and use of the E2C2 system will result in improvements in implementation and clinical outcomes.

Specific Aim 3. Conduct a mixed methods evaluation to detect, understand and reduce disparities in the adoption and implementation of the E2C2 intervention among elderly and rural-dwelling patients with cancer.

Background:

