A version of the statistical model above was fit to 79 weeks of preliminary baseline data (i.e., with no intervention effect X_{kt}) in order to estimate the parameters (e.g., $\boldsymbol{\nu}_A, \boldsymbol{\Sigma}_A$) needed to simulate longitudinal data for the 15 clusters. Clusters were randomly allocated to the steps in **Figure 1**, and treatment effects due to intervention were generated on a grid of eight values $\nu_{1B} = 0.00, 0.01, 0.02, 0.03, 0.05, 0.10, 0.15, 0.20$, with the remaining $\nu_{2B} = \nu_{3B} = \nu_{4B} = \nu_{5B} = 0$ to assume the most conservative case (i.e., only a single symptom is affected by the intervention). The cluster effects were then generated according to $\boldsymbol{B}_k \sim N(\boldsymbol{\nu}_B, \sqrt{\nu_{1B}} \boldsymbol{\Sigma}_A)$. This data generation process was used to simulate 100 data sets under each of the eight grid values for ν_{1B} . The full model above was then used to estimate $\boldsymbol{\nu}_B$ and test the hypothesis that all $\nu_{jB} = 0$, via simultaneous credible bounds.⁹⁷ The results are provided in **Figure 3**. As can be seen in the figure, the test keeps very close to the nominal level (i.e., 0.01, 0.05, or 0.10, respectively) when there is no effect. However, the power rises quickly to detect even a small average score difference of even 0.10 with 70% power (at 0.05 LOS) and a difference of 0.20 with nearly 100% power.

Data Analysis Plan:

Specific Aim 1 Analyses.

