\mathbf{Q} is a vector representing the secular time effect, where q_{jmk} is the calendar quarter; and, the time elapsed since encounter $j-1$; for $j=2,\dots$

In addition

A_{ikm} is a vector of random effects, $[A_{1km},\dots,A_{5km}]$ specified as varying across patients nested within clusters

$$A_{ikm} \sim [A_i + \alpha_{ikm} + \gamma_{im}]; \quad i=1,\dots,6$$

$$[\alpha_{ikm}] \sim N(0, \Sigma_\alpha)$$

$$[\gamma_{im}] \sim N(0, \Sigma_\gamma)$$

where Σ s are exchangeable correlation matrices.

μ_{imw} , $i=1,\dots,6$ is a discrete-time vector of random effects for each cluster m and step w ; and,

ν_{it} , $i=1,\dots,6$ is a multivariate autoregressive process of order 1, AR(1) with Gaussian noise, to account for time dependent correlation of responses within each patient over time; and,

Prior to estimating this model, the distributions of the SPPADE scores will be examined and, if appropriate, transformed to have approximately normal distributions. Covariates will be similarly reviewed and either transformed or categorized before inclusion in the model.

In general, fitting the above models (1) which has several random effects (in both time and across clusters) can be challenging. However, Markov Chain Monte Carlo estimation is very effective at fitting such models and are appropriate for assessing stepped-wedge cluster randomized designs.⁹⁹ Moreover, by incorporating historical time trends into our priors for the effect of calendar time, a Bayesian model can increase statistical power relative to a frequentist approach.¹⁰⁰ All other priors will be flat. In the event that model (1) can't be estimated, we will simplify the error structure and other features using review of variable distributions and correlations, including intra-cluster correlations and time dependent correlation, to inform the simplifications. Then, using our final model we will calculate posterior probabilities and credible intervals to assess whether coefficients differ from zero; specifically, we will achieve the primary aim of the study by calculating the posterior probabilities that each of B_1, \dots, B_6 is greater than 0; we will accept that the intervention is effective if $PP[\text{abs}(B_i) > 0, i=1,\dots,6] \geq 0.80$.

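### The rule for declaring the intervention effective (H1a, repeated for H1b) is satisfied by every possible data set, has no direction, and is not the test that was powered

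*Combined protocol and SAP*

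**What the plan says.** Under Hypotheses H1a (Data Analysis Plan, Specific Aim 1 Analyses), model (1) is to be fitted by MCMC. Calendar time gets an informative prior, and for the rest "All other priors will be flat". The analysts will "calculate posterior probabilities and credible intervals to assess whether coefficients differ from zero". They will compute the posterior probability that each of B_1 to B_6 exceeds zero, and then "we will accept that the intervention is effective if" "PP[\text{abs}(B_i) > 0, i=1,\dots,6] \geq 0.80".

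Hypotheses H1b adds an indicator of an elevated prior score and its interaction D_i with the intervention. It is tested in the same way, on the absolute value of D_i, and no threshold is restated.

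The cluster-period model, which becomes the primary analysis if the survey-level model cannot be computed, has no acceptance rule of its own.

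The Power Statement uses another procedure. It tests that all effects are zero "via simultaneous credible bounds" and reports that "the test keeps very close to the nominal level" (0.01, 0.05 or 0.10) when there is no effect. Power is 70% for a difference of 0.10 and nearly 100% for 0.20, at level 0.05, with one symptom affected.

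The aim itself has a direction: the intervention "will significantly reduce SPPADE symptom and physical dysfunction scores".

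**The concern.** A posterior statement that an absolute value is greater than zero carries no information when the parameter is continuous, so a threshold placed on it cannot separate success from failure. The absolute value also removes the sign. The signed quantity mentioned just before the rule does not rescue it. That quantity has no threshold, and on scales where a high score is bad, a coefficient above zero means worsening.

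What is at stake is the formal claim for both primary hypotheses. Posterior estimates and credible intervals would still show sign and size. But if a working rule is chosen after the results are known, the error rate of the primary claim is undefined.

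**Working it through.** **1. The rule as written.** Inputs: continuous B_i and a flat prior (Hypotheses H1a). A continuous posterior puts no mass on a single point, so P(B_i = 0 | data) = 0 and P(|B_i| > 0 | data) = 1. This holds for each score and for all six jointly. A simulation with six correlated normal posteriors gave probability 1.000 at true effects of 0, −0.1, −0.2, +0.2 and +1.0, and acceptance in 1,000 of 1,000 data sets with no effect. The same argument applies to D_i.

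**2. The stated power, checked against itself.** It cannot be reproduced, because no variances, correlations or survey counts are printed. A normal approximation shows that it is plausible for its own test. With 70% power at 0.10, SE = 0.10/(z_crit + 0.524).
- Two-sided 0.05, no adjustment: 0.10/(1.960 + 0.524) = 0.040. Power at 0.20 is Φ(0.20/0.0403 − 1.960) = 0.9987.
- Bonferroni over the five effects listed there: 0.10/(2.576 + 0.524) = 0.032. Power at 0.20 is 0.9999.

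Both agree with the plan's nearly 100%. These figures describe the simultaneous-bounds test. The written rule has power and type I error both equal to 100%.

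**3. A directional rule that keeps 0.80.** With a flat prior and a normal estimate, P(B_i < 0 | data) = Φ(−z_i), so one score passes by chance 20% of the time. The plan does not say how the six combine. The table assumes no effect on any score and equal correlation ρ between the six estimates (assumed; not in the documents).

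| ρ | any one passes | all six pass | joint probability ≥ 0.80 | any-of-six threshold for 5% one-sided | for 2.5% |
|---|---|---|---|---|---|
| 0 | 0.738 | 0.00006 | <0.0001 | 0.9915 | 0.9958 |
| 0.3 | 0.605 | 0.005 | 0.0006 | 0.9906 | 0.9955 |
| 0.5 | 0.522 | 0.018 | 0.005 | 0.9891 | 0.9949 |
| 0.7 | 0.434 | 0.045 | 0.023 | 0.9859 | 0.9935 |

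At ρ = 0 the first two entries are 1 − 0.8⁶ = 0.738 and 0.2⁶ = 0.00006.

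**4. The same readings in the plan's own power scenario.** One symptom improves by 0.10, with SE 0.040. The chance of acceptance is 0.95 to 0.98 for any one, 0.0003 to 0.052 for all six, and under 0.001 to 0.025 for joint. No reading gives both a 0.05 level and 70% power.

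**5. H1b.** In model (2) the effect in patients with an elevated prior score is B_i + D_i. Apply a directional 0.80 rule to D_i alone:
- B_i = −0.20, D_i = 0, so elevated patients benefit by 0.20. The pass rate is 1 − 0.80 = 20% per symptom, whatever the SE.
- B_i = +0.20, D_i = −0.10, so elevated patients worsen by 0.10. The pass rate is Φ(0.10/SE − 0.842), which is 0.88 at SE 0.05 and 0.66 at SE 0.08 (both SEs assumed).

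**The case against.** The strongest reply is that the formula is a slip. The sentence speaks of credible intervals and of coefficients differing from zero, so a sensible analyst would not apply it literally. That is probably true, but the intended rule cannot be recovered. No interval level or interval criterion for acceptance is set.

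Second, the notation puts all six scores inside one probability, which favours a joint or all-six reading. A directional 0.80 rule would then have a false-positive rate below 5%. This is fair, and the 43% to 74% figures belong only to the any-one reading. But the all-six and joint readings have almost no power when a single symptom responds, which is the case the trial was powered for.

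Third, Hypotheses H1b opens by asking about a differential effect, for which D_i is the right coefficient. This stands as a reading of that section. It conflicts with the Aims and with the introduction to the Aim 1 analyses, which define H1b as the effect among patients with moderate or worse symptoms. The plan also expects little effect in patients with mild or no symptoms. If B_i in model (2) is near zero, D_i and B_i + D_i nearly coincide. The H1b percentages therefore show what the rule permits, not what is expected.

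Fourth, the H1a rule could be taken to carry over to the fallback model. That is reasonable, but what carries over is the same empty rule. The Power Statement gives no power for H1b, so the mismatch with the powered test is a point about H1a.

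**Conclusion.** The concern holds. The H1a rule is met with certainty for any data, does not distinguish benefit from harm, and is not the test behind the stated power. H1b inherits the defect if the 0.80 carries over, and it also tests the interaction where the Aims name the effect in elevated patients. These conclusions need only continuous posteriors without a point mass at zero, which flat priors imply.

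The error rates of possible repairs depend on the assumed correlations (0 to 0.7) and on normal estimates. The H1b percentages depend on assumed SEs and illustrative effects. None of these assumptions is needed to show that the rule is void. It must be corrected before the primary result is declared.

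**What to change.** **H1a.** Replace the rule with a directional one. The simplest choice is the Power Statement's simultaneous credible bounds at a named level, requiring the upper bound for B_i to lie below zero. The alternative is P(B_i < 0 | data) at or above a threshold calibrated by simulation. For an any-of-six rule that is about 0.986 to 0.992 for 5% one-sided, or 0.994 to 0.996 for 2.5%. State whether any one score, all six or a joint probability decides. Base the calculation on six scores, since the Power Statement lists five effects. Confirm that any scores "transformed to have approximately normal distributions" keep their direction, and report P(B_i > 0) as evidence of harm.

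**H1b.** Apply the same rule, with its threshold restated, to B_i + D_i. Report D_i separately as the differential effect.

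**Fallback.** State that the same rule applies to the cluster-period model.

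**Cost.** The change needs SAP wording, dated and justified as a change to the primary criterion, and no new data or patients. The simultaneous-bounds route is the cheaper one. A calibrated threshold can start from the existing simulation set-up but needs more than its 100 data sets per value, because the Monte Carlo SE at a 5% error rate is √(0.05 × 0.95/100) = 2.2 percentage points. As a rough guide, with SE 0.032 to 0.040 the 5% any-of-six threshold detects a 0.10 benefit on one symptom about 55% to 80% of the time, and 0.20 over 99%. That range straddles the stated 70%. It assumes one constant SE, whereas the plan's simulation lets cluster variability change with effect size, so power should be re-simulated under the final rule.

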The E2C2 trial takes advantage of our growing recognition of the interrelatedness of symptoms, as its targeting of commonly co-occurring symptoms will enhance our understanding of symptom clusters. Emerging research demonstrates the substantial co-occurrence of cancer-related symptoms and, consequently, the impracticality and, indeed, artificiality of evaluating and treating symptoms in isolation⁵⁴⁻⁶¹ rather than in clusters such as the SPPADE grouping (Sleep disturbance, Pain, Anxiety, Depression, and Energy deficit/fatigue), which represents a prevalent and potentially treatable group of overlapping symptoms.^{54,56,57,59,62-67} Cross-sectional analyses will provide insights into the co-occurrence rates of these 5 symptoms as well as their individual and additive effects on functional status and quality of life. Longitudinal analyses will determine the responsiveness of individual symptoms and overall symptom burden to treatment as well as patient- and disease-specific mediators and moderators of improvement.

The E2C2 trial is clinically and methodologically significant because it will comprehensively evaluate the use of ubiquitous and inexpensive EHR functionalities – automated assessment, decision support, and implementation – to enhance symptom control. While these capabilities are increasingly EHR agonistic, our utilization of Epic may be particularly beneficial as it is used across 250 U.S. healthcare organizations and as 65% of the US population has an Epic record, and 69 million Americans have Epic My Chart accounts.⁶⁸ The Epic internal logic, assessment, audit and feedback, and alert functionalities used in the E2C2 intervention are straightforward to configure, requiring only 1 to 2 weeks of builder time, thereby limiting the human resource requirements for E2C2 intervention implementation. As noted above, these capabilities are increasingly EHR agonistic and while build specifics will differ in Cerner, Meditech, and other EHRs, the fundamental principles will remain constant.⁶⁹ Our detailed Resource Sharing Plan emphasizes the development of manuals that outline build specifics that will be pertinent to both Epic and non-Epic using organizations.

This strategy has the potential to radically accelerate the uptake and broad implementation of E2C2 capabilities with limited resource investment.

Study Design and Methods

Methods:

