
The primary outcomes of the trial are a bundle of 6 SPPADE symptom and function scores assessed with numerical rating scales (NRSs) collected in association with medical oncology clinic appointments. The primary analysis will test differences in the change in mean joint SPPADE symptom NRS scores in all participants, and in those who experience elevated (4-10/10) symptoms, between participants who are exposed to the intervention and those who are not. Secondary outcomes will include PROMIS-CAT measures for anxiety, depression, pain, and physical function, assessed up to every four months depending on visit frequency. Additional secondary outcomes will include health care utilization, adherence to cancer treatment, and survival. Variation in ePRO response rates and outcomes will be assessed for all participants, but special emphasis will also be given to disparities in outcomes among elderly and rurally based patients.

Process measures will capture stakeholders' use of the EHR graphic and decision support tools and will be abstracted from the EHR. All analyses will be performed using methods appropriate for cluster randomized stepped wedge trials. In parallel with conduct of the E2C2 trial, mixed methods will be used to comprehensively assess system usability, multi-stakeholder experience, and barriers and facilitators for stakeholders' use of the system. Qualitative interviews will also

be conducted to understand possible reasons for disparities in the adoption and implementation of the E2C2 intervention among elderly and rural-dwelling patients with cancer.

Cancer Patient Enrollment: This is a population-based study, where all eligible patients seen by clinicians at the Medical Oncology Clinic in Rochester and hematology/oncology in the Midwest Mayo Clinic Health Systems (MCHS) will be enrolled. This inclusive enrollment approach substantially increases the generalizability and external validity of our real-world pragmatic trial. Rochester campus will act as primary research site and there will be no study team responsibilities at any of the MCHS sites.

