Triage to Level 1 or 2. Patients' responses to the BSFS questionnaire will initially assign symptomatic patients to one of 2 incremental Levels of stepped care. Patients will be triaged to Level 1 (moderate symptoms) unless they meet Level 2 (severe symptoms) criteria based on SPPADE symptom or physical dysfunction intensity; non-response to treatment; patient preference for SCM contact; or clinician referral. Patients may move between the "no symptom" state and Levels 1 and 2, as depicted in, depending on treatment response, and symptom onset and/or worsening.

Dispensing of self-management education modules. A second algorithm, irrespective of Level assignment, will determine which self-management education modules (also referred to as "Symptom Toolkits") will be automatically dispensed to symptomatic patients either via their web portal, where they will be directed to the E2C2 patient facing website (cancersymptoms.mayoclinic.org) or in print. Each printed symptom toolkit will contain an assortment of patient education and IRB approved materials in paper and digital form. Patients' preferences for mode of delivery will be electronically captured in their EHRs. Criteria that will determine whether and which materials are dispensed include symptom number and type, and request for reissue.

Order pre-configuration for first-line symptom management. A third algorithm for patients triaged to Level 2 will identify first-line, guideline-supported prescriptive interventions *matched to those listed in the self-management modules* and will automatically present these to the clinicians as pre-configured orders.

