We will summarize patient-, cluster-, and survey-level characteristics (e.g., sex, age, cancer type and stage, insurance status) by intervention status (pre-E2C2, E2C2) of the encounter. All analyses will be conducted on an intention to treat basis. The primary analysis will test differences in change in joint SPPADE symptom NRS scores in all participants, and in those who report elevated (4-10/10) symptoms, between participants who are exposed to the intervention and those who are not. We have two primary hypotheses. The first will assess the effect of the intervention across the full cohort of patients enrolled, Hypothesis *H1a*. The second will assess the effect of the intervention among patients who report moderate or worse symptoms, Hypothesis *H1b*. The rationale for Hypothesis *H1b* is that some intervention components are only offered to participants who report elevated symptom scores. Additionally, a large proportion of the trial cohort will only report mild or no symptoms. Among these participants there is little or no opportunity to improve symptoms and no practical exposure to the intervention. The original hypotheses regarding population-level effects will retain primary importance, yet it is critical to test intervention effects in the subset of patients that ever have elevated symptom scores.

We will include a common set of variables in all models testing the effectiveness of the intervention. Cancer type and stage will be included, as well as 7 variables selected as likely to impact the use of the portal and completion of the

[figure not shown]

Figure 3. Power simulations for E2C2 Interventions

surveys: from the EHR we will capture age (categorized into 10-year increments), sex (male or female), and severity of illness (Elixhauser score as a categorical variable). We will also link the patient 9-digit zip code to Census data to get estimates of educational level, income, and broadband access, which will be categorized into quartiles.

Hypotheses H1a

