In the event that the model with patient surveys as the unit of analysis cannot be computed, we will use an alternative cluster-period model for the primary analysis. We will aggregate outcomes and covariates for each cluster for each time period and use these cluster-level estimates to assess the effect of the intervention. We will calculate the mean of each of the 6 different SPPADE NRS scores collected during trial cluster-periods. We will also calculate the mean baseline score for each participant that reports one or more ePROMs. We will then test the first primary hypothesis using a multivariate regression model using these 15 clusters \times 6 period = 90 cluster-period values, including an indicator for intervention status for each cluster-period, and adjusting for mean baseline scores and including indicators for study step to account for secular trends and for indicators for cluster to account for cancer type. We will adjust for cluster-period averaged values of factors of patients reporting during each period for which the SMD between intervention and control cluster-periods are >0.2 .

To assess the robustness of using the CP model, we will replicate the main analyses for each symptom NRS score. We will use the originally specified generalized mixed effects model, as well as the CP model adapted to the univariate dependent variable. This former model will be estimated at the survey level, with random effects for surveys within patients and patients within clusters; these 6 models (one for each symptom score) also included all pre-specified patient covariates, baseline symptom score, the lag in weeks since the baseline measurement and the interaction of the lag time with the baseline effect.

Because there is potential for the intervention to impact the baseline scores as well, we will replicate the cluster-period and survey level models each symptom score, including patients with only 1 survey score.

We will estimate models using the STAN software package.

Hypotheses H1b

To test whether the intervention has a differential effect on those patients with at least one elevated symptom score,

we will construct an indicator, E_{ijkm} , varying by measurement time, which indicates whether the i^{th} prior symptom score was elevated (>3). By interacting these indicators with the main intervention effects B_i we can assess the impact of the intervention on the corresponding scores of patients with at least one elevated score:

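### H1b concerns the intervention effect in patients with elevated symptoms (B_i + D_i in model (2)), but the planned criterion looks only at the interaction D_i

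*Combined protocol and SAP*

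**What the plan says.** Three places state H1b as an effect within a subgroup:

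- Specific Aim 1, H1b: "Among patients who report moderate or worse symptoms, SPPADE symptom scores will improve more for patients who have been exposed to the intervention".
- Overall Study Design, on the primary analysis: "and in those who experience elevated (4-10/10) symptoms, between participants who are exposed to the intervention and those who are not".
- Specific Aim 1 Analyses, which calls H1b one of two primary hypotheses: "The second will assess the effect of the intervention among patients who report moderate or worse symptoms". It adds that "it is critical to test intervention effects in the subset of patients that ever have elevated symptom scores".

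The Hypotheses H1b section opens with a different question: "To test whether the intervention has a differential effect on those patients with at least one elevated symptom score". Model (2) adds to the H1a model an indicator E, set to 1 when the prior score on the same symptom exceeded 3, and its product with the intervention indicator X. The criterion is PP[Abs(D_i) > 0, i = 1,…,6], where D_i is the coefficient of E × X. The 0.80 threshold comes only by back-reference to H1a. If model (2) cannot be fitted, a cluster-period model is used that includes a post-elevation indicator and its interaction with intervention. The text does not say which coefficient of that model is tested.

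**The concern.** A test of D_i asks whether the effect differs between elevated and non-elevated prior scores. H1b asks whether patients with elevated symptoms do better when exposed. D_i can be zero while those patients benefit, and non-zero while they do not. H1a does not fill the gap, because it concerns the whole cohort. Followed as written, the plan would answer an effect-modification question and report it as the result of a primary hypothesis.

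**Working it through.** **1. Contrast.** The intervention terms in model (2) are B_i X + D_i E X.

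- Effect when E = 0: B_i.
- Effect when E = 1: B_i + D_i.
- Difference between the two: D_i.

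So H1b under this model is B_i + D_i. A least-squares fit to 200,000 simulated records confirms it. With true B = −0.3 and D = 0, the fitted D was −0.010, while the fitted B + D was −0.317, equal to the direct exposed-minus-unexposed difference in the elevated group. With B = +0.3 and D = −0.3, the fitted D was −0.307, while the effect in the elevated group was −0.012.

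**2. Is B_i = 0 a safe premise?** Specific Aim 1 Analyses leans that way. Of participants with only mild or no symptoms it says: "Among these participants there is little or no opportunity to improve symptoms and no practical exposure to the intervention". But E = 0 is not that group. E is set symptom by symptom, so a patient with high pain and low sleep disturbance has E = 0 for sleep. That patient is still symptomatic, and the questionnaire responses "will initially assign symptomatic patients to one of 2 incremental Levels of stepped care". The Background says: "Emerging research demonstrates the substantial co-occurrence of cancer-related symptoms". The education booklet also goes to every patient, whatever their Level.

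To gauge the overlap, assume six exchangeable latent normal scores, each elevated with probability p. The share of E = 0 records from patients elevated on another symptom is then:

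| Assumed p | Correlation 0.7 | Correlation 0.5 | Correlation 0.3 |
|---|---|---|---|
| 0.20 | 29% | 40% | 51% |
| 0.40 | 48% | 63% | 76% |

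**3. The plan's own figures.** The Power Statement gives 70% power at a difference of 0.10 and nearly 100% at 0.20, for the main effect. It gives nothing for H1b. Its simulation parameters are not listed, so it cannot be rebuilt. Its two points do agree: SE = 0.10/(1.960 + 0.524) = 0.040, and power at 0.20 is Φ(0.20/0.0403 − 1.960) = 99.9%.

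**4. Illustration, one score.** As printed, PP[Abs(D_i) > 0] equals 1 for any continuous posterior, so some replacement is needed in any case. Assume a one-directional rule at 0.80 and a flat-prior normal posterior. Then P(pass) = Φ(|effect|/SE − 0.8416), for an effect that is zero or in the direction of improvement. The effect sizes come from the Power Statement; the SEs are assumed.

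| True effect | SE 0.06 | SE 0.08 | SE 0.12 |
|---|---|---|---|
| 0 | 20% | 20% | 20% |
| 0.10 | 80% | 66% | 50% |
| 0.20 | 99% | 95% | 80% |

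- Benefit missed: B_i = −0.20 and D_i = 0, so the sum is −0.20. The rule on D_i passes 20%; the rule on the sum passes 99%, 95% or 80%.
- Benefit wrongly credited: B_i = +0.10 and D_i = −0.10, so the sum is 0. The rule on D_i passes 80%, 66% or 50%; the rule on the sum passes 20%.

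**5. Combining six scores.** This does not bear on D_i versus the sum, but the replacement rule must settle it. With all six effects zero, equal SEs and assumed correlation 0.3 to 0.6, requiring PP[all six < 0] ≥ 0.80 passes 0.1% to 1%. Requiring at least one score with PP ≥ 0.80 passes about 61% to 48%.

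**6. Who is elevated?** Model (2) uses the prior score on the same symptom. The sentences introducing it speak of at least one elevated score. The fallback uses any earlier elevated score. Specific Aim 1 Analyses says ever elevated. Model (2) and its fallback would therefore test H1b in different groups.

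**The case against.** The strongest reply is that the subgroup effect was plainly intended. The H1b section says the interaction allows the impact in patients with an elevated score to be assessed, and B_i + D_i can be computed from the same draws. That shows intent, but the stated criterion still omits B_i.

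Next, B_i may be close to zero. Later education modules are matched to the symptoms a patient rates moderate or worse, and a low score has little room to fall. Being triaged for pain is not the same as being treated for sleep. This is fair, and the overlap shares above do not show that B_i differs from zero. But the model leaves B_i free, and a primary test should not rest on an unstated assumption that it is zero.

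Three further points stand as qualifications.

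- The fallback leaves its tested coefficient unnamed; it does not name the wrong one.
- The wrongly credited case needs the intervention to worsen low-score records (B_i = +0.10). It also gives D_i the same SE as the sum. If the strata are independent, SE(D) = SE(B + D)/√(1 − p), which is 1.12 to 1.41 times larger for p = 0.20 to 0.50. The 80%, 66% and 50% then become 63–74%, 52–61% and 40–46%. Shared cluster-period terms could instead make SE(D) smaller.
- The plan gives the population-level hypotheses greater weight than H1b. It still calls H1b primary.

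**Conclusion.** The concern holds and should be fixed before analysis. The mismatch follows from the plan's own equation and needs no assumed number: a primary hypothesis has no planned test of the effect it states. The pass rates are illustrations that rest on assumed SEs and on a directional rule the plan does not contain; the overlap shares rest on assumed prevalences and correlations. If B_i were exactly zero, the two rules would target the same quantity. The definition of elevated is a related but separate defect: B_i + D_i is the H1b effect only for the group that E defines.

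**What to change.** In the Hypotheses H1b section:

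1. Base the criterion on the posterior of B_i + D_i in the direction of improvement (below 0), from the same MCMC draws.
2. State there the threshold and how the six scores combine (all, any, or another rule), in the same way as for H1a.
3. Report D_i with its credible interval as a secondary analysis of effect modification. Give it a symbol of its own, since D also denotes the strata effects.
4. In the cluster-period fallback, name the same sum: intervention plus interaction coefficient.
5. Use one definition of elevated in model (2) and the fallback, reconciled with the ever-elevated and at-least-one wordings. The choice is the sponsor's, noting that an indicator based on scores after go-live can itself be affected by the intervention.

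Restating H1b as a differential-effect hypothesis would also make hypothesis and test agree. It would, however, change a primary hypothesis stated in Specific Aim 1, Overall Study Design and Specific Aim 1 Analyses.

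The cost is SAP wording. The sum comes from the same model fit; at most, the cluster-period means are re-split for the fallback.
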